### **Prior, Concomitant, and Further Therapies**

Prior, concomitant, and further therapies (drug and non-drug treatments) will be coded by the World Health Organization (WHO) medical dictionary. Listings of prior, concomitant, and further therapies will be provided separately.

## **6.2. Analysis of Primary Endpoint**

### **6.2.1. DLT(Part 1)**

Dose Limiting Toxicity (DLT) is the primary endpoint of the dose escalation component of the study, which will be summarized by dose level using the Per Protocol Analysis Set for patients in the dose escalation portion of the study. A listing of the DLTs will also be provided. If necessary, a summary and listing of AEs meeting the criteria for DLT by malignancy may be provided using the Per Protocol Analysis Set for patients in the MTD expansion portion of the study.

### **6.2.2. Safety Endpoints (Part 1 and Part 2)**

#### **Adverse Events**

Adverse Events (AEs) will be graded by the investigator according to the CTCAE version 4.03 and coded using the MedDRA. The focus of AE summaries will be on Treatment Emergent Adverse Events, those with initial onset or increasing in severity after the first dose of study medication. The number and percentage of patients who experienced any AE, serious AE (SAE), treatment related AE, and treatment related SAE will be summarized according to worst toxicity grades. The summaries will present AEs both on the entire study period and by cycle (Cycle 1 and Cycles beyond 1) for overall and each dose. The Safety Analysis Set will be used. Part 1 and Part 2 data will be summarized separately and will also be pooled together for analysis. Pfizer standard on safety data reporting will be followed.

#### **Laboratory Tests Abnormalities**

The number and percentage of patients who experienced laboratory test abnormalities will be summarized according to worst toxicity grade observed for each laboratory test for overall and each dose. The analyses will summarize laboratory tests both in the entire study period and by cycle (Cycle 1 and Cycles beyond 1). Shift tables will be provided to examine the distribution of laboratory abnormalities. The Safety Analysis Set will be used.

For laboratory tests without CTC grade definitions, results will be categorized as normal, abnormal high/low or not done.

## **Vital signs**

The number and percentage of patients who experienced vital signs abnormalities will be summarized (See Schedule of Activities in the protocol for details and [Appendix 2](#)).

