Height	X									
Weight	X	X			X				X	
Vital signs ⁴	X	X	X	X	X	X	X	X		X
Performance status ⁵	X	X			X			X		X
Contraception check	X	X			X			X		
Laboratory										
Unique screening laboratory tests ⁶	X									
Hematology ⁷	X	X	X	X	X	X	X	X		X
Blood Chemistry ⁸	X	X	X	X	X	X	X	X		X
Coagulation ⁹	X	X		X	X	X		X		X
Urinalysis ¹⁰	X	X		X	X	X		X		X
Pregnancy test ¹¹	X	X			X			X		

		Treatment Period							Post Treatment	
		Cycle 1 (1 cycle = 21 days)				Cycles ≥ 2			End of Treatment ²¹	Follow-up ²²
		Day 1	Day 4	Day 8	Day 15	Day 1	Day 8	Day 15		
Visit Identifier	Screen ¹ (≤28 days prior to registration)									
Visit Window (days)				(±1)	(±1)	(±1)	(±2)	(±2)		
(12 lead) ECG ¹²	X	X		X	X	X	X	X (Cycle 2 only)	X	
Registration and Treatment										
Registration ¹³		X								
Study treatment ¹⁴		X		X	X	X	X	X		
Inpatient Monitoring ¹⁵		X		X ¹⁵						
Tumor assessments										
CT or MRI scan or equivalent ¹⁶	X					X (every 6 weeks beginning at Cycle 3 and then every 12 weeks beginning at Cycle 8)			X ¹⁶	
Other samplings										
CCI										
CCI										
Blood samples for PF-06671008										
Blood sample for Anti-PF-06671008 Antibody										
CCI										
Other clinical assessments										
Adverse events ¹⁸		X	X	X	X	X	X	X	X	X
Concomitant Treatments ¹⁹	X	X	X	X	X	X	X	X	X	X
Ophthalmic Examination ²⁰	X									

* Visit windows are calculated off the first day of each cycle. See [Dose Delays](#) section for calculation of visit windows for Cycle 1.

Abbreviations: CT = computed tomography; ECG = electrocardiogram; MRI = magnetic resonance imaging

1. **Screening:** to be obtained within 28 days prior to registration.
2. **Informed Consent:** must be obtained prior to undergoing any study specific procedures. May be obtained more than 28 days prior to registration.
3. **Complete Physical Examination:** No need to repeat on Cycle 1 Day 1 (C1D1) if screening assessment is performed within 3 days of dosing.
4. **Vital Signs:** Includes temperature (oral, tympanic, temporal or axillary), blood pressure (BP) and pulse rate to be recorded in a supine or seated position. On each dosing day, vitals should be measured prior to infusion start (pre-dose) and at the end of the PF-06671008 infusion. In addition, pulse oximetry is to be collected on dosing days prior to infusion start (pre-dose) and at the end of the PF-06671008 infusion as part of the vital sign evaluation.
5. **Performance Status:** Use Eastern Cooperative Oncology Group (ECOG). – see [Appendix 3](#).

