5.4.1. Cytokine Release Syndrome

Symptoms associated with CRS vary greatly and may be difficult to distinguish from other conditions. The more common symptoms include fever, nausea, headache, tachycardia, hypotension, rash and shortness of breath. The severity of symptoms can be mild to life threatening and thus, there should be a high suspicion for CRS if these symptoms occur. Grade 1 CRS does not require any intervention but patients should be monitored closely. Grade ≥ 2 CRS requires PF-06671008 infusion interruption and prompt symptomatic treatment per local standard of care. For CRS not rapidly responsive to supportive care or CRS of Grade ≥ 3 , treatment with corticosteroids and/or tocilizumab,² an anti-human IL-6R mAb, should be considered.¹² A suggested treatment algorithm for the management and grading of CRS based on a revised CRS grading system by Lee et al. is provided in [Appendix 8](#).

The decision to incorporate pre-medication (ie, corticosteroids) for CRS prophylaxis in all patients will be made following discussions between the sponsor and the investigators. The pre-treatment medication will not be supplied by Pfizer.

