7.1. Safety Assessment

Safety assessments will include collection of adverse events (AEs), serious adverse events (SAEs), vital signs (including pulse oximetry) and physical examination, electrocardiogram (ECG [12-lead]), laboratory assessments, including pregnancy tests and verification of concomitant treatments.

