### 3.2. Secondary Endpoint (s)

- *Adverse Events as characterized by type, frequency, severity (as graded by National Cancer Institute Common Terminology Criteria for Adverse Events (NCI CTCAE) v.4.03) timing, seriousness, and relationship to study therapy;*
- *Laboratory abnormalities as characterized by type, frequency, severity (as graded by NCI CTCAE v.4.03) and timing;*
- *Vital sign abnormalities;*
- Pharmacokinetic parameters of PF-06671008 Single Dose (SD) -  $C_{max}$ ,  $T_{max}$ ,  $AUC_{sd,\tau}$ ,  $t_{1/2}$ ,  $AUC_{inf}$ , and CL for intravenous (IV) administration or apparent clearance (CL/F) for subcutaneous (SC) administration as data permit. Multiple Dose (MD) (assuming steady state is achieved) -  $C_{max,ss}$ ,  $T_{max,ss}$ ,  $AUC_{ss,\tau}$ ,  $t_{1/2}$ ,  $C_{min,ss}$ , CL for IV or CL/F for SC, volume of distribution ( $V_{ss}$ ) for IV or apparent volume of distribution at steady state ( $V_{ss}/F$ ) for SC, and  $R_{ac}$  ( $AUC_{ss,\tau}/AUC_{sd,\tau}$ ) as data permit;
- Incidence and titers of anti-drug antibodies (ADA) and neutralizing antibodies against PF-06671008;
- *Objective response, as assessed using the RECIST version 1.1 – Part 1 only;*
- *Progression Free Survival (PFS) and Overall Survival (OS) – Part 2 only.*

CCI

CCI

Covariates may also be considered when exploring QTc and PK relationship.

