### Categories for Vital Signs

Systolic BP (mm Hg)	min. $<$ 90	
Systolic BP (mm Hg) change from baseline	max. decrease $\geq$ 30	max. increase $\geq$ 30
Diastolic BP (mm Hg)	min. $<$ 50	
Diastolic BP (mm Hg) change from baseline	max. decrease $\geq$ 20	max. increase $\geq$ 20
Supine pulse rate (bpm)	min. $<$ 40	max. $>$ 120

Measurements that fulfil these criteria are to be listed in the study report.

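### The vital-sign abnormality endpoint has no class for temperature or oxygen saturation, so recorded fever and desaturation are left out of its table and listing

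*SAP*

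**What the plan says.** SAP 3.2 lists "Vital sign abnormalities" as a secondary endpoint. The analysis, in SAP 6.2.2 under Vital signs, is one sentence: "The number and percentage of patients who experienced vital signs abnormalities will be summarized", with a pointer to the protocol's Schedule of Activities and to SAP Appendix 2.

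Appendix 2 (Categories for Vital Signs) has rows for systolic pressure, diastolic pressure and a pulse row whose label begins "Supine pulse rate (bpm". It then asks for measurements that meet these criteria to be listed in the study report.

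The protocol's definition of vital signs is wider. Footnote 4 of the IV Schedule of Activities reads: "Includes temperature (oral, tympanic, temporal or axillary), blood pressure (BP) and pulse rate to be recorded in a supine or seated position". The same footnote adds pulse oximetry on dosing days as part of the vital-sign evaluation, and the SC schedule does likewise. Protocol 7.1 counts among the safety assessments "vital signs (including pulse oximetry) and physical examination".

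On cytokine release syndrome (CRS), protocol 5.4.1 says: "The more common symptoms include fever, nausea, headache, tachycardia, hypotension, rash and shortness of breath". The CRS grading in protocol Appendix 8 uses a pulse oximeter reading below 88% as an example of hypoxia at Grades 2 and 3.

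**The concern.** An endpoint that counts patients with an abnormality needs a definition of abnormal for each measurement it covers. Here the protocol collects four kinds of vital sign and the SAP defines abnormal for two. The two left undefined matter for this drug: fever comes first in the protocol's list of common CRS symptoms, and oxygen saturation is part of its CRS grading. A by-dose summary of measured temperature and saturation would describe the milder range of these effects without relying on anyone's decision to report an event. The plan collects the readings but gives them no place in the endpoint.

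**Working it through.** No sample size, error rate or formula is involved, and the plan gives no figure to reproduce. The check sets what is collected beside what is classed.

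| Vital sign | Collected (Schedules of Activities, footnote 4; protocol 7.1.4) | Class in SAP Appendix 2 |
|---|---|---|
| Blood pressure | Yes, supine or seated | Systolic: minimum <90, decrease ≥30, increase ≥30 mm Hg. Diastolic: minimum <50, decrease ≥20, increase ≥20 mm Hg |
| Pulse rate | Yes, supine or seated | Minimum <40, maximum >120 bpm, under a supine label |
| Temperature | Yes | None |
| Oxygen saturation | Yes, on dosing days | None |

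**Count.** Appendix 2 holds 3 + 3 + 2 = 8 criteria, none of them for temperature or saturation. Of four kinds of vital sign, two have classes and 4 − 2 = 2 have none.

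**Is the gap filled elsewhere?**
- The Schedules of Activities give timing and method, but no abnormality limit for temperature or saturation.
- Protocol 9.6.2 describes adverse-event and laboratory analyses and says nothing on vital signs.
- SAP 6.2.2 has a fallback for laboratory tests without a CTC grade (normal, abnormal high or low, not done). Vital signs have none.
- The SAP's reference to the sponsor's reporting standard is in the adverse-event paragraph and gives no vital-sign class.

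**The pulse label.** The blood-pressure rows, such as "Systolic BP (mm Hg) change from baseline" and "Diastolic BP (mm Hg) change from baseline", name no position, although pressure too may be taken supine or seated. Only the pulse row does. Nothing in the SAP says that seated readings are to be dropped, so the label is ambiguous and is not an exclusion rule.

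**What added rows could show.** On dosing days, IV vital signs and oximetry are scheduled before the infusion and at its end. In SC cohorts both are scheduled before the injection only. In-patient monitoring follows local practice, with no stated requirement to record those readings as scheduled vital signs. New rows would therefore capture part of the acute effect, and the SC saturation row very little of it.

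**Can the protocol's own limits be reused?** Only with a label. Protocol 3.3 defines the fever part of febrile neutropenia as a single temperature above 38.3 °C, or a temperature of at least 38 °C sustained for more than an hour. Protocol Appendix 8 excludes transient falls below 88% from CRS grading. A single reading at either limit is therefore not the same thing as meeting those criteria.

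**The case against.** The strongest reply is that little is lost. Fever, hypoxia and CRS reach the adverse-event tables, which SAP 6.2.2 summarises by worst grade, by cycle and by dose. The study tests no hypotheses (SAP 5.1), and this is one descriptive secondary table in a final analysis run after the last subject's last visit. Most of this stands, and it limits the weight of the point. It does not close the gap. Under protocol 8.5 an abnormal finding becomes an adverse event only if it has symptoms, needs further testing or intervention, changes dosing or treatment in specified ways, or is judged to be one. A measured-value endpoint exists to complement that judgement; if adverse-event reporting were enough, the pressure and pulse classes would be unnecessary too.

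A reader might infer several stronger conclusions that the documents do not support:
- **That dose decisions are affected.** DLTs follow protocol 3.3, and the priming-dose guidance in 3.2.1 rests on CRS events, mainly by grade and duration. Neither uses this table, and safety review of individual data is ongoing (protocol 9.7).
- **That temperature and saturation are the only CRS signals free of investigator attribution.** Blood pressure and pulse are measured and classed. C-reactive protein is a scheduled test and is required when CRS is suspected; laboratory abnormalities are summarised by dose.
- **That seated tachycardia is excluded.** Only the label suggests it. An analyst would probably apply the limits to any recorded pulse.
- **That low saturation is among the common CRS symptoms listed.** Section 5.4.1 lists shortness of breath; saturation enters through the grading in Appendix 8.
- **That febrile patients would be reported as having no fever.** A sign without a class is not tabulated at all, which is an omission and not a false zero.

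**Conclusion.** The point holds as a completeness gap in a named secondary safety endpoint. Two of the four kinds of vital sign that the protocol collects have no abnormality class, and a third carries a position label narrower than the protocol allows. Followed as written, the SAP leaves recorded fever and desaturation out of the vital-sign table and the listing it specifies. Hypotension and pulse above 120 bpm are covered.

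The number of patients affected cannot be derived, because the documents give no rate of fever or desaturation and scheduled readings would catch only some episodes. The conclusion assumes that Appendix 2 is the operative definition of abnormal, as SAP 6.2.2 implies; no other definition appears in either document. The change is worth making because it is cheap and fever is a leading sign of the drug's recognised risk, but the gap does not threaten the dose-finding.

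**What to change.** Amend SAP Appendix 2 and the vital-signs sentence in SAP 6.2.2:

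1. Add a maximum-temperature class, for example ≥38.0 °C and >38.3 °C, and a minimum-saturation class, for example <88%. The sponsor may set other limits, but some must be stated.
2. Label both as descriptive single-reading measurement classes. State that they are neither CRS grades nor febrile-neutropenia criteria, because the protocol's sustained-temperature condition and its exclusion of transient falls are not applied.
3. Relabel the pulse row as pulse rate, supine or seated.
4. Tabulate the vital-sign classes by dose and route. The present sentence names no grouping, whereas the adverse-event and laboratory paragraphs do.
5. Footnote the timing: on dosing days, IV readings before and at the end of infusion; SC oximetry before injection only. State that the rows understate acute events.

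The cost is two table rows and some wording. No new data are needed, and patient care is unchanged. The downside is that fever or desaturation from other causes, such as infection or tumour, is also counted, just as the existing pressure and pulse classes count changes of any cause.

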### **6.3. Analysis for Secondary Endpoints**

#### **6.3.1. Efficacy Endpoints Analysis**

In this Phase 1 study efficacy is a secondary objective for Part 1. The efficacy analysis will be performed in the mITT population. Part 1 and Part 2 data will be summarized separately and will also be pooled together for analysis. Efficacy will be analyzed separately from those assessed by RECIST **CCI** criteria for solid tumor.

Efficacy data in Part 1, Part 2 and across the two Parts may be summarized in the following groups:

- Overall summary for all doses and all tumor types assessed by RECIST **CCI** criteria;
- Same tumor type regardless of dose;
- Same dose regardless of tumor type;
- Same dose and same tumor type if data permit.

Summary tables of best Overall Response Rate, Progression Free Survival, and Overall Survival (for Part 2), duration of stable disease (DOSD), and duration of response (DOR) will be provided by the groups aforementioned. Efficacy listings will be provided that include best response, first CR/PR date, last date with CR or PR, most recent date without progression, progression date, death date, date of first response and last tumor assessment date, etc. Swimmer plot for individual clinical response and time on treatment, waterfall plot for individual tumor size percent change from baseline, and spider plot for individual tumor size percent change from baseline over time will be presented.

The following table provides an overview of the efficacy analysis.

Endpoint	Analysis Set	Statistical Method	Model/ Covariates/ Strata	Missing Data
Overall response	mITT	Exact CI	See aformentioned summary descriptions on data pooling across dose and tumor type	Observed case
Overall Survival	ITT	Kaplan-Meier	See aformentioned summary descriptions on data pooling across dose and tumor type	Censored at last visit
Progression Free Survival (PFS)	mITT	Kaplan-Meier	See aformentioned summary descriptions on data pooling across dose and tumor type	Censored per Appendix 1
Time to Progression (TTP)	mITT	Kaplan-Meier	See aformentioned summary descriptions on data pooling across dose and tumor type	Censored per Appendix 1
Duration of Response (DOR)	mITT	Kaplan-Meier	See aformentioned summary descriptions on data pooling across dose and tumor type	Censored per Appendix 1
Duration of Stable Disease (DOSD)	mITT	Kaplan-Meier	See aformentioned summary descriptions on data pooling across dose and tumor type	Censored per Appendix 1

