15. **Inpatient Monitoring:** Patients receiving PF-06671008 intravenously will be admitted for inpatient monitoring for at least 24 hours following the first administration of study treatment (C1D1). For patients enrolled in cohorts where Dose Prime will be given on C1D1 followed by a higher dose on C1D8, patients will also be admitted for inpatient monitoring for at least 24 hours (for cohorts evaluating IV route of administration) following the second dose (C1D8). Patients may be released only after the investigator has confirmed the patient has not exhibited signs of a cytokine reaction. Patients should complete the required study specific laboratory assessments as detailed in the [Schedule of Pharmacokinetic, CCI \[REDACTED\] Assessment](#) table and should be monitored per local standard practice for inpatient monitoring. At doses of 100 ng/kg or higher, especially when the total dose exceeds 10,000 ng, additional in-patient overnight observation for subsequent doses beyond C1D1 may be considered based on the investigator's discretion and should be discussed with Pfizer.

16. **Tumor Assessments:** Tumor assessments will include all known or suspected disease sites. Imaging may include chest, abdomen and pelvis CT or MRI scans or equivalent. The same modality should be completed, if possible throughout the study. Bone scans will be performed at baseline if disease is suspected and on study as appropriate to follow disease. Baseline central nervous system (CNS) imaging is not required with the exception of symptomatic patients to rule out CNS metastases; patient ineligible if positive for CNS metastases. CT or MRI scans to be done every 6 weeks (± 7 days) from the start of study treatment until disease progression by irRECIST or death, or until permanent discontinuation of study treatment. The frequency will change to every 12 weeks (± 7 days) beginning at Cycle 8. Response (complete response (CR)/partial response (PR)) and disease progression will be confirmed with two consecutive timepoints at least 4 weeks apart (in the absence of rapid clinical deterioration for progression). Tumor assessments should be fixed according to the calendar, regardless of treatment delays. Tumor assessments should be repeated at the End of Treatment visit if more than 6 weeks have passed since the last evaluation.

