22. **Follow-Up:** At least 28 days, and no more than 35 days, after discontinuation of treatment, patients will return to obtain these assessments as well as evaluate the resolution of any treatment-related toxicity. Patients continuing to experience toxicity at this point following discontinuation of treatment will continue to be followed at least every 4 weeks until resolution or determination, in the clinical judgment of the investigator, that no further improvement is expected. Subsequent to the Follow-Up visit, patients should be contacted by telephone every 8 weeks (± 7 days) to obtain information on subsequent anti-cancer treatment and overall survival for up to two years from the date of randomization.

Schedule of Pharmacokinetic, CCI**Assessments for Intravenous Administration –****Cohort 1 Only**

Visit Identifier	Screen	Cycle 1												Cycle 2						Subsequent Cycles			EOT				
		1	2	4	8	24	72	0	1	2	4	8	24	72	0	1	0	1	4	24	72	0	1	0	1	0	1
Study Day																											
Hours Pre-/Post-Dose*		0	1	2	4	8	24	72	0	1	2	4	8	24	72	0	1	0	1	4	24	72	0	1	0	1	
CCI																											
Blood samples for PF-06671008		X	X	X	X	X	X	X	X	X	X	X	X	X	X	X	X	X	X	X	X	X	X	X	X	X	
Blood samples for Anti-PF-06671008 Antibody		X																									X
CCI																											
CCI																											

Schedule of Pharmacokinetic, CCI Cohort 2 and Beyond and Part 2

Assessments for Intravenous Administration – Part 1

SCHEDULE OF ACTIVITIES FOR SUBCUTANEOUS ADMINISTRATION

The schedule of activities table provides an overview of the protocol visits and procedures. Refer to the **ASSESSMENTS** section of the protocol for detailed information on each assessment required for compliance with the protocol.

The investigator may schedule visits (unplanned visits) in addition to those listed on the schedule of activities, in order to conduct evaluations or assessments required to protect the well-being of the patient.

Visit Identifier	Screen ¹ (≤28 days prior to registration)	Treatment Period										Post Treatment	
		Cycle 1 (1 cycle = 21 days)						Cycles ≥2					
		Day 1	Day 2	Day 3	Day 5	Day 8	Day 15	Day 1	Day 2	Day 8	Day 15	End of Treatment ²²	Follow-up ²³
Visit Window (days)					(±1)	(±1)	(±1)		(±2)	(±2)			
Informed consent ²	X												
Tumor history	X												
Medical history	X												
Complete physical examination	X	X ³										X	
Abbreviated physical examination					X	X	X		X	X			X
Height	X												
Weight	X	X						X				X	

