9.1. Analysis Sets

Data analysis will be performed on the following analysis populations:

1. Safety analysis set.
 - The safety analysis set includes all enrolled patients who receive at least one dose of study treatment.
2. Full analysis set.
 - The full analysis set includes all enrolled patients.

3. Per-protocol analysis set (evaluable for MTD).

- The per protocol analysis set includes all enrolled patients who receive at least one dose of study treatment and who do not have major treatment deviations during first cycle. Patients with major treatment deviations during the first cycle of treatment are not evaluable for the MTD assessment and will be replaced as needed to permit MTD estimation. Major treatment deviations include failure to satisfy major entry criteria (eg, confirmation of the target disease; signed informed consent) or use of other anticancer treatments during the active treatment and disease follow-up phases other than as defined/allowed in this protocol.

[figure not shown]
4. Modified Intent-to-Treat (mITT) Population.

- The modified intent-to-treat (mITT) is the analysis population that will follow the ITT principle and include patients receiving at least 1 dose of study medication with baseline assessment and at least 1 post baseline assessment, disease progression, or death before the first tumor assessment. The mITT population may be used for interim analysis and conference presentations when the study is still ongoing.

5. PK analysis sets.

- The PK parameter analysis population is defined as all enrolled patients treated who have sufficient information to estimate at least 1 of the PK parameters of interest and who have no major protocol deviations influencing the PK assessment.

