#### Primary Endpoint (Part 2)

- *Objective response (OR) as determined by the Response Evaluation Criteria in Solid Tumor (RECIST) version 1.1 criteria ([Appendix 3](#)).*

[figure not shown]

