#### 4.6. Modified Intent-to-Treat Set

*The modified intent-to-treat (mITT) population is defined as all the randomized subjects who have received at least 1 dose of study medication, have measurable disease baseline assessment (within 28 days prior to study entry) and at least 1 post baseline assessment or disease progression or death before the first tumor assessment. The mITT population may be used for interim analysis and conference presentations when the study is still ongoing.*

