#### **4. Recording Tumor Assessments**

All sites of disease must be assessed at baseline. Baseline assessments should be done as close as possible prior to study start. For an adequate baseline assessment, all required scans must be done within 28 days prior to treatment and all disease must be documented appropriately. If baseline assessment is inadequate, subsequent statuses generally should be indeterminate.

*Note: For the patient population being evaluated in this protocol, the baseline assessment may be completed within 6 weeks prior to randomization.*

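### The Part 2 response rate leaves treated but unscanned patients out of its denominator, and no readable text counts them as non-responders

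*SAP*

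**What the plan says.** SAP 3.1 defines the Part 2 primary endpoint as "Objective response (OR) as determined by the Response Evaluation Criteria in Solid Tumor (RECIST) version 1.1 criteria". SAP 6.2, on the primary endpoint, covers only DLTs and safety. Response is handled in SAP 6.3.1, where "The efficacy analysis will be performed in the mITT population". The overview table there gives overall response the mITT set, an exact confidence interval and "Observed case" for missing data. The same table uses ITT for overall survival.

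Besides a dose and a baseline assessment, SAP 4.6 requires "at least 1 post baseline assessment or disease progression or death before the first tumor assessment" for mITT. Protocol 9.1 is close to this: "at least 1 post baseline assessment, disease progression, or death before the first tumor assessment". The SAP version adds measurable disease and a baseline within 28 days of study entry. Both documents mention mITT for interim analyses and conference presentations, while SAP 5 plans no interim analysis.

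SAP 5.4.1 deals with incomplete dates, and SAP 5.4.2 gives listings plus censoring for time-to-event endpoints. Neither covers missing response in the readable text.

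SAP 5.2.3 adds a posterior-probability summary of response per indication, assessed once at least 10 patients are enrolled. SAP 2.3 and 5.2.2 instead count evaluable patients, a term not defined for response.

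**The concern.** A patient treated in Part 2 who stops for toxicity, refusal or loss to follow-up before any post-baseline scan, without progression or early death, meets none of the mITT conditions. That patient was exposed and has no recorded response, yet is removed from the rate instead of being counted as a non-responder. The effect on the primary endpoint is one-sided.

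Two related ambiguities add to this. Because "Observed case" is undefined, it is not certain how patients kept in mITT without a usable response (death before the first scan, or indeterminate status only) enter the rate. And because the posterior summary counts enrolled patients in one place while the enrolment guidance counts evaluable ones elsewhere, the same data can give two answers to the low-activity question.

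**Working it through.** **Can a patient leave unscanned?** The protocol's Schedule of Activities says "Tumor assessments should be repeated at the End of Treatment visit if more than 6 weeks have passed since the last evaluation". The period after first dose in which stopping triggers no rescan is therefore 42 days minus the age of the baseline scan at first dose:

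- scan 28 days old: 42 − 28 = 14 days
- scan 1 day old: 42 − 1 = 41 days

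Under the 28-day baseline rule, the End of Treatment scan leaves a gap of roughly the first 14 to 41 days. SAP Appendix 3 also says "the baseline assessment may be completed within 6 weeks prior to randomization", which conflicts with the 28-day condition in SAP 4.6.

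**Effect on the response rate.** With r responders among n treated, of whom d are unscanned, the mITT rate is r/(n − d), which is at least r/n. Take n = 20, the top of the planned range per indication, and assume r = 6. The documents give no value for d, so 0, 1 and 3 are assumptions. Intervals are exact (Clopper-Pearson) 95%.

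| Unscanned d | Losses not replaced: reported rate (all-treated 6/20 = 30.0%) | Losses replaced to reach 20 evaluable: all-treated rate (reported 6/20 = 30.0%) |
|---|---|---|
| 0 | 6/20 = 30.0% (11.9 to 54.3) | 6/20 = 30.0% |
| 1 | 6/19 = 31.6% (12.6 to 56.6) | 6/21 = 28.6% (11.3 to 52.2) |
| 3 | 6/17 = 35.3% (14.2 to 61.7) | 6/23 = 26.1% (10.2 to 48.4) |

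The overstatement is 1.6 points (31.6 − 30.0) or 1.4 points (30.0 − 28.6) with one loss, and 5.3 (35.3 − 30.0) or 3.9 (30.0 − 26.1) with three.

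**The plan's posterior figures.** With the Jeffreys prior, P(ORR < c) is the Beta(r + 0.5, n − r + 0.5) distribution function at c.

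- 1/10: P(ORR < 30%) = 0.926 (plan 0.93).
- 7/20: P(ORR ≥ 30%) = 0.696 (plan 0.70) and P(ORR < 20%) = 0.054 (plan 0.05).
- P(ORR < 20%): 0/10 gives 0.968, 1/10 gives 0.774, 0/16 gives 0.993, 1/16 gives 0.929 and 2/16 gives 0.764. All exceed 0.75, as the plan states.

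The plan's figures therefore reproduce.

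**Effect on the low-activity flag, P(ORR < 20%) > 0.75.** Suppose one of the treated patients counted was never scanned:

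- 1 responder among 10 treated: 0.774, flag met. Drop the unscanned patient: 1/9 gives 0.728, not met.
- 2 responders among 16 treated: 0.764, flag met. Drop the unscanned patient: 2/15 gives 0.726, not met.

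In these examples the choice of denominator decides on which side of the plan's threshold the indication falls.

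**The case against.** The best case for the plan is that the excluded group is small. mITT already keeps patients with progression or early death. Protocol 7.4 calls for imaging on suspicion of progression, whatever the time since the last scan. Protocol 6.4 asks that patients who miss visits return for a final one, and SAP Appendix 3 asks sites to try to document progression after treatment stops. Telephone contact covers "overall survival for up to two years from the date of randomization", and on a literal reading of mITT a patient who later dies unscanned may come back in. Part 2 is exploratory, SAP 5.1 states no hypotheses, the activity rules are permissive, and listings would show each case. All of this stands. It limits the size of the problem but does not supply a rule for the rate.

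It is also fair that the natural reading of the SAP 6.3.1 table makes mITT the denominator, so that early deaths and indeterminate patients count as non-responders. A reader might infer that the plan drops them. The text does not say so, and defining the term would settle it.

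Three other inferences are not supported:

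- *A gap starting at day 0.* This needs a 42-day-old baseline scan, and such a patient fails the SAP's 28-day mITT condition whatever happens later.
- *A 10-point overstatement.* This needs 5 of 20 patients (25%) unscanned, giving 6/15 = 40.0%. Nothing in the documents suggests that rate.
- *That the denominator cannot affect the flag.* Adding an unscanned patient to a flagged 1/10 gives 1/11 and 0.812, so the flag stays. But adding a non-responder can only raise P(ORR < 20%), so this checks only the direction that cannot reverse.

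Parts of SAP 5.3 and 5.4.2 are redacted, so the statement that no rule exists is confined to the readable text.

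**Conclusion.** The point holds on the readable text. The exact-interval estimate of the Part 2 primary endpoint is specified only in mITT with an undefined missing-data rule, and treated patients excluded for want of any post-baseline assessment can only push ORR up or leave it unchanged. The posterior summary is a second stated analysis of response, but its denominator is inconsistent.

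The size rests on assumed losses. It is zero if nobody leaves unscanned, about 1.4 to 1.6 points with one loss and 3.9 to 5.3 points with three, on 6 responders and 20 patients. One loss is small beside an interval of 11.9% to 54.3%. The clearest practical consequence is that one exclusion can cross the 0.75 mark at 1/10 or 2/16, although that mark only may inform a judgement. The importance is modest, but the text should be corrected because it governs a primary endpoint in an open-label study and the correction is cheap.

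**What to change.** In SAP 6.3.1, define the primary Part 2 ORR per indication as the proportion of responders among all treated patients, using the Safety Analysis Set of SAP 4.2, with an exact 95% interval. State that patients with no adequate post-baseline response assessment count as non-responders, and put that rule in place of "Observed case". Keep the mITT rate as a sensitivity analysis.

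Use the same denominator for the posterior summary in SAP 5.2.3, and align with it the wording on the first 10 evaluable patients in SAP 2.3 and 5.2.2 and protocol 3.5 and 9.3. Reconcile the 28-day and 6-week baseline statements at the same time.

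The cost is a possibly slightly lower reported ORR, text edits, and possibly a protocol amendment, since SAP 2 says major changes to the primary endpoint's analysis will be reflected in one. No new data are needed.
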